5.2 Exclusion criteria

A subject will not be eligible for inclusion in this trial if any of the following criteria apply:

- 1. Bilateral ISSNHL;
- 2. Acute hearing loss from noise trauma, barotrauma or head trauma;
- 3. Air-bone gap higher than 20 dB at the average of 3 contiguous frequencies below 4 kHz, when the air-bone gap is measurable;
- 4. History of autoimmune hearing loss, radiation-induced hearing loss, endolymphatic hydrops or Menière's disease in either ear;
- 5. History of chronic inflammatory or suppurative ear disease or cholesteatoma in the affected ear;
- 6. Current evidence or history of acoustic neuroma or other retrocochlear damage in the affected ear;
- 7. History of otosclerosis in the affected ear;
- 8. Suspected perilymph fistula or membrane rupture in the affected ear;

- 9. Congenital hearing loss;
- 10. History of ISSNHL in the past 2 years;
- 11. Otitis media or otitis externa that is ongoing or ended within 7 days prior to study treatment;
- 12. Radiation therapy in the head and neck area within the past 5 years;
- 13. Abnormality of the tympanic membrane in the affected ear that would preclude intratympanic administration:
- 14. Any pre-treatment or ongoing treatment for ISSNHL-related hearing loss or tinnitus (except for oral corticosteroid background therapy that was started within 36 hours prior to randomization);
- 15. Any other planned pharmacological or non-pharmacological treatment for hearing loss or tinnitus for the duration of the trial;
- 16. Any therapy known as ototoxic (e.g. aminoglycosides [systemic or ototopical with middle ear exposure], cisplatin, loop diuretics, quinine etc.) in the 3 months prior to treatment visit;
- 17. History within the past 2 years or presence of drug abuse or alcoholism;
- 18. Subjects with diagnosed anxiety disorders, psychosis, depression, schizophrenia, attempted suicide or other significant psychiatric conditions that can impact their ability to cooperate and comply with the study protocol;
- 19. Subjects who have answered "yes" to Suicidal Ideation question 4 or 5 of the C-SSRS;
- 20. Any clinically relevant autoimmune, respiratory, cardiovascular, neurological disorder (except vertigo or tinnitus) or other abnormality that in the opinion of the Investigator may pose a safety risk to a subject in this study, which may confound efficacy or safety assessment, or may interfere with study participation;
- 21. Known HIV, hepatitis B or hepatitis C, or symptomatic herpes zoster infection;
- 22. Women who are breast-feeding, pregnant or who are planning to become pregnant during the study;
- 23. Women of childbearing potential who are unwilling or unable to use an effective method of avoiding pregnancy from screening until the end of the study (FUV4). Effective methods of avoiding pregnancy are contraceptive methods with a Pearl index of less than 1 when used consistently and correctly (including implantable, injectable, oral and transdermal contraceptives, intrauterine devices, diaphragm with spermicide, male or female condoms with spermicide, or cervical cap, or a sterile sexual partner, or being abstinent);
- 24. Concurrent participation in another clinical study or participation in another clinical study within 30 days prior to randomization (TV).

5.3 Discontinuation of IMP treatment and subject withdrawal from the trial

5.3.1 Screening failures

Screening failures are subjects who have been enrolled in the trial (i.e. ICF signed), but discontinue the trial during TV before randomization for whatever reason (withdrawal of consent, not meeting eligibility criteria, by decision of Investigator, etc.). For screening failures, no further procedures should be performed.

5.3.2 Withdrawals

The Investigator should make all efforts to keep a subject in the trial.

Withdrawals are subjects who have been enrolled in the trial (i.e. ICF signed), but discontinue the trial after randomization. This may occur under the following circumstances:

- 1. The subject withdraws his/her informed consent to participate in the clinical trial. Subjects have the right to prematurely withdraw from the trial at any time and without any obligation to justify their decision;
- 2. The subject is lost to follow-up;
- 3. Subject's death;
- 4. The Investigator does not consider trial participation to be in the subject's best interest.

Any reasons for withdrawal after randomization must be documented carefully in the subject's medical records and in the case report form (CRF). If possible, the subject should attend a premature end of trial visit (see Section 7.4), which follows the course of assessments scheduled for FUV4.

A subject is considered lost to follow-up when the Investigator cannot reach the subject or, if contact details are available and permission has been obtained, the subject's relatives should be contacted by phone to obtain a reason for the subject not to attend a visit (e.g. an AE). If at least 6 phone calls or other contact efforts (e.g. e-mails, text messages) at different times of the day during a course of three weeks are not answered, a registered letter should be sent to the patient. All contact attempts should be documented in the patient's source documents. If the subject prefers to withdraw due to an AE, the Investigator should try to motivate the subject to continue until the event has stabilized with no further change expected, or the Investigator states the AE is not clinically significant and no further follow-up is required, but still encouraged. If the subject returns to the site at a later time point, the Sponsor should be informed to discuss further steps.

5.4 Termination of the trial

5.4.1 Regular termination of trial

The clinical trial will be considered complete once all randomized subjects have completed the study.

5.4.2 Premature trial termination

Subject enrolment and randomization will be stopped if, based on a review of safety and tolerability data by the Sponsor, further study treatments are deemed not acceptable.

The Sponsor reserves the right to discontinue the trial at any time and for any reason. In the event of emerging evidence from literature or other scientific sources demonstrating that the investigational drug may be ineffective or may affect the subjects' safety, the Sponsor will decide about trial termination.

In addition, the Sponsor reserves the right to discontinue a trial site in case of major protocol deviation or insufficient enrolment.

6 Trial procedures

6.1 Principal Investigator and trial team

The Principal Investigator may delegate trial specific tasks to other members of the trial team. The delegation must however be documented in writing prior to the involvement of the team member. The Principal Investigator is responsible for appropriate training of his/her team members on the trial specific requirements prior to their involvement in the trial in accordance with GCP and local regulations. The Sponsor and/or the Clinical Research Associate (CRA) may assist the Principal Investigator in staff training and may provide supporting training material. Training shall be documented adequately.

Any trial team member performing trial specific assessments and procedures must be qualified and licensed professionally where applicable and according to the local standard medical practice.

All procedures should first be documented in the source documents (e.g. subject's medical file) before being transcribed into the CRF.

6.2 Schedule of visits

A schedule of visits and trial assessments is provided in the Protocol Summary (Table 1) and in Section 7.

6.3 Informed Consent

The currently valid IRB/IEC approved version of the participant information sheet and informed consent form (ICF) will be used to inform the subject about the trial and to document the subject's agreement to participate in the trial. The Investigator, or designee, will obtain a written, dated, timed and signed ICF from each subject prior to performing any trial-specific procedure on the subject. The informed consent process will be documented in the source documents. The Investigator will retain the original copy of the signed ICF, and a copy will be provided to the subject.

The Investigator will ensure that appropriate processes and procedures are in place to ensure that ongoing questions and concerns of enrolled subjects are adequately addressed and that the subjects are informed of any new information that may affect their decision to continue participation in the clinical trial.

Depending on local requirements, routine standard of care assessments prior to ICF signature might not need to be repeated to reduce the burden to the subject under the following circumstances:

- Assessment was done as standard of care regardless of potential study participation.
- Assessment was done on the day of study treatment.
- For pure tone and speech audiometry, assessments were done not more than 2 hours prior to ICF signature and within 5 hours to IMP administration (i.e. study treatment must be done within 5 hours from pure tone and speech audiometry).

Standard of care routine assessments are:

- Demography/baseline characteristics
- Medical history (incl. hearing loss onset)
- Prior and concomitant medication recording
- Tinnitus evaluation
- Vital signs
- Otoscopy/microscopy
- Tympanometry
- Spontaneous nystagmus
- Balance test
- Pure tone and speech audiometry.

NOTE: Section 13.4 of this protocol should be referred to as the subjects go through the informed consent process prior to their participation in the trial.

6.4 Allocation of subject number

After informed consent is obtained, the subject will be assigned a subject number which serves as unique subject identifier. Upon randomization an IMP kit number will be assigned to the subject.

6.5 Baseline Assessments

6.5.1 Inclusion and exclusion qualification

Each subject will be screened and must meet all inclusion criteria and none of the exclusion criteria to qualify for randomization. To verify eligibility, each subject will be asked the specific questions outlined in the inclusion/exclusion criteria by an authorized trial team member; the answers will be documented in each subject's source documents. Documentation of audiology reports, laboratory reports and other source documents are to be filed with the subject's records.

6.5.2 Demographics and baseline characteristics

Demographic and baseline characteristics including but not limited to age, gender, and race/ethnicity, will be recorded in the subject's source documents and entered into the CRF as per local requirements.

6.5.3 Medical history, prior and concomitant medication

The patient's medical history, including a detailed otolaryngological history, will be taken at the TV and documented in the subject's record. Medical history that is clinically relevant will be recorded in the CRF.

Any drug known as ototoxic taken up to 3 months before randomization (TV) should be recorded in the CRF. Any medication that is ongoing or was taken within 2 weeks prior to randomization should be recorded in the CRF. This includes prescription medicines as well as non-prescription medicines, herbal medicines and vitamins and mineral supplements.

The local anesthetic selected and used by the Investigator in preparation of the intratympanic administration procedure for application of the IMP will not be recorded as concomitant medication, but will be recorded separately with the IMP administration in the CRF.

6.5.4 Hearing loss onset

The time of the subject's ISSNHL onset will be recorded at the TV prior to randomization, rounded to the nearest hour. For example if the hearing loss occurred at 6:29 am then 6 am will be recorded; in case of 6:30 or 6:45 am, 7 am will be assigned.

If no precise time is known, the following assumptions will be made:

• "Morning": between 6 am and noon; midpoint at 9 am

• "Afternoon": between noon and 6 pm; midpoint at 3 pm

• "Evening": between 6 pm and midnight; midpoint at 9 pm

• "Night": between midnight and 6 am; midpoint at 3 am

6.5.5 Tinnitus history and characteristics

At TV, the concept of tinnitus will first be explained by the Investigator to the subject with a description of the symptom, and the presence or absence of tinnitus will be assessed (see Appendix 1). If tinnitus is present, tinnitus history (onset, tinnitus inducing event, laterality) will be recorded at TV and tinnitus characteristics (persistence, pitch, sound) will be recorded at all visits (except cFUV).

6.5.6 Physical examination

At TV a general physical examination will be conducted by the Investigator or designee. This examination serves to detect obvious and severe abnormalities, which are to be documented on the respective CRF page. The physical examination should be performed prior to the final determination of the subject's eligibility (in particular to support the evaluation of exclusion criterion 20). Body height and body weight will also be recorded.

6.6 Safety Assessments

6.6.1 Vital signs

Sitting blood pressure will be taken with the same arm at each visit (except cFUV). The arm should be positioned at heart level using the same sphygmomanometer at each visit. The subject should be seated for approximately 5 minutes prior to measurement. Vital signs (blood pressure and pulse) and body temperature will be measured at each visit.

6.6.2 Blood testing

A blood sample will be drawn at TV and at FUV1 and shipped for evaluation to the central laboratory. A manual will be provided containing trial specific instructions for handling and shipping of the sample. The Investigator should review the central laboratory report for any out of range values and their clinical relevance promptly upon receipt, and confirm the review by signing and dating the report. Virology and HbA_{1c} will be assessed at TV only.

The following parameters will be tested:

Hematology

- Hemoglobin (Hgb),
- Hematocrit (Hct),
- Red blood cell (RBC),
- White blood cell (WBC),
- Platelets (Plt),
- WBC differential.

Biochemistry

- Sodium (Na),
- Potassium (K),
- Chloride (Cl),
- Glucose,
- Glycated hemoglobin (HbA_{1c})
- Blood urea nitrogen (BUN),
- Creatinine (CRE),
- Calcium (Ca),
- Phosphorus (P),
- Uric acid (UA),
- Alanine aminotransferase (ALT),
- Aspartate aminotransferase (AST),
- Gamma-glutamyl transpeptidase (γ-GTP),
- Lactate dehydrogenase (LDH),
- Alkaline phosphatase (ALP),
- Total bilirubin (T-bil),
- Total protein (TP),
- Albumin (Alb).

Virology:

- Human immunodeficiency virus (HIV),
- Hepatitis B (HBV),
- Hepatitis C (HCV),
- Herpes Zoster (Varicella).

Should the laboratory report be incomplete or non-analyzable, a retest should be done as soon as possible

It is the responsibility of the Investigator to assess if an abnormality on the central laboratory report is to be considered as clinically significant or not. All laboratory values that, in the Investigator's opinion, show any clinically significant abnormality must be reported as an AE and will be subject to follow-up by the Investigator.

Refer to the corresponding manual for further details.

6.6.3 Pregnancy test

Women of childbearing potential will have a urine pregnancy test performed with a urine dipstick at the site prior to randomization. This test must be negative for the subject to be randomized and to receive IMP. The pregnancy test will be repeated at FUV4.

6.6.4 Questionnaires and numerical rating scales

Questionnaires and numerical rating scales will be administered as outlined in Table 1. At all follow-up visits they must be completed at applicable visits prior to performing the audiology assessments. At Treatment Visit, the questionnaires may be completed after audiology assessment, but have to be completed in any case prior to IMP administration. Subjects should be seated in a quiet environment and have ample time for completion. A member of the study team will explain the purpose and use of the assessment, but subjects should complete the questionnaires on their own without being influenced or directed by the study team member. Subjects should however have the chance to ask questions and ask for assistance, should this be required. Responses from the previous visit will not be accessible for subjects or made available to them.

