	All continuous efficacy data will be summarized descriptively by treatment group and time point including changes from baseline (n, arithmetic mean, standard deviation, minimum, Q25, median, Q75 and maxi-
	mum),

[figure not shown]

Table 1: Schedule of visits and assessments

	TV	FUV1	FUV2	cFUV ¹	FUV3	SC	FUV4 ²
Study visit assessment	(D0)	(D3±1)	(D7±2)	(D14±3)	(D28±5)	(D56±7)	(D91±7)
Informed consent	0						***
Inclusion and exclusion criteria	•						
Demography/baseline characteristic							
Medical history (incl. hearing loss onset)	•						
Prior and concomitant medication recording		6	•	•	•	6	0
Tinnitus evaluation (history, characteristics)		•3	• ³		•3		• ³
Physical examination							
Vital signs (blood pressure, temperature, pulse)		•	•		•		0
Laboratory test (hematology, biochemistry)		•					
Laboratory test (virology)							
Urine pregnancy test, if applicable							•
HHIA questionnaire					•		0
PGIC _{hearing loss} Scale			•		•		0
Tinnitus presence or absence and numerical rating scales (TLQ _{Loudest} , TAQ _{Worst})			Subject diary				
Otoscopy/microscopy	•	•	0	•	•		•
Tympanometry			• ⁴	•4	0		•
Pure tone audiometry (air and bone conducted)		•	0		•		•
Speech audiometry (WRS at 80 dB in quiet)	• ^{5,6}		6		•		0
Speech audiometry (WRS at 60 dB in quiet)	• ^{5,6}						8
Spontaneous nystagmus (Frenzel goggles or VNG)	• ⁵	0	•		•		•
Balance test (Romberg's test)	•5	8	0		•		6
Suicidality questionnaire (C-SSRS)			6		6		
Final eligibility check prior to randomization	0						· · · · · · · · · · · · · · · · · · ·
Randomization							
IMP intratympanic injection	6						
Background therapy (corticosteroid) ⁷	•						
Dispense background therapy documentation card ⁷	•						
Check completion of background therapy documentation card ⁷		•	•	•	•		
Adverse event reporting	•	•	•	•	•	•	•

Only to be performed if eardrum is not closed at FUV2 at D7.

² Or premature end of trial visit in case the subject terminates the trial prematurely.

³ Only to be performed if tinnitus is present.

⁴ Only to be performed if eardrum is fully closed.

⁵ Assessment to be repeated, at the earliest, 24 hours from onset if subject presenting within the first 24 hours from ISSNHL onset. If eligibility is confirmed, this second assessment serves as baseline measure.

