6.6.5.3 Pure tone audiometry

Air and bone conduction hearing thresholds will be tested at all visits (excluding cFUV).

All tests will be performed by certified audiologists or adequately trained site staff and conducted in a sound attenuated booth/room with doors closed, using standard earphones or earphone inserts.

Compliance with relevant standards will be verified and documented during source data verification. In order to assure overall quality and consistency, individual or all pure tone audiometry data may be reviewed by an independent expert designated by the Sponsor.

Timing of Baseline Assessment

Results of audiograms previously performed as part of routine clinical practice at the investigational site should not be older than 2 hours prior to signing the ICF, and 5 hours prior to the IMP administration (i.e. study treatment must be done within 5 hours from pure tone audiometry) to be considered valid for baseline, otherwise the measures have to be repeated. Pure tone audiograms performed for subjects presenting within the first 24 hours from ISSNHL onset have to be confirmed by a new assessment that is conducted at the earliest 24 hours after onset of ISSNHL. The high possibility of spontaneous remission early after ISSNHL onset may otherwise lead to the inclusion of patients who would recover on their own. The new confirmatory measure will serve as baseline value.

Assessment of Hearing Thresholds

Hearing thresholds will be determined by pure tone audiometry in both ears at 0.25, 0.5, 1, 2, 3, 4, 6, and 8 kHz (air conduction), and at 0.5, 1, 2, 3, 4 kHz (bone conduction) in accordance with ISO standard 8253-1 and any other relevant standards.

For each frequency, hearing threshold is to be determined by (A) approaching the hearing threshold in 20 dB steps, followed by (B) fine tuning steps in 5 dB steps or smaller. Fine tuning determination occurs by detecting, at least twice, the level at which the subject no longer hears the tone and the level at which the subject starts to hear the tone. The hearing threshold is defined as the lowest tone level at which the test subject hears the tone, and which is confirmed by a second measure.

Determination of the three most affected contiguous frequencies

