7.1 Baseline assessment, randomization and treatment

After having obtained informed consent from the subject, the baseline assessment begins at the treatment visit (TV) prior to randomization and IMP administration. It ends once all pre-randomization assessments have been completed. No trial specific procedure must be performed before the subject and the Investigator, or designee, have signed and dated the ICF. Signing the ICF defines the start of the trial. The time of signing the ICF and of the baseline assessments should be recorded in the source documents and on the CRF. Please refer to section 6.3 for details on timing of baseline assessments.

The required procedures may be done on different calendar days, however the day of randomization and treatment (IMP administration) is considered Day 0 (D0).

After ICF signature and prior to randomization, the following baseline assessments will be performed:

- Inclusion and exclusion criteria qualification (see 6.5.1.);
- Demography/baseline characteristics;
- Medical history;
- Hearing loss onset;
- Prior and concomitant medication;
- Tinnitus evaluation (history and characteristics);
- General physical examination, body weight, height;
- Vital signs (blood pressure, temperature, pulse);
- Tinnitus presence or absence and numerical rating scales;
- Otoscopy/microscopy;
- Tympanometry;
- Pure tone audiometry (air and bone conducted)*;
- Speech audiometry $(WRS_{(80 \text{ dB})} \text{ and } WRS_{(60 \text{ dB})})^{**}$;
- Spontaneous nystagmus (Frenzel goggles)**;
- Balance test (Romberg's test)**;
- Suicidality questionnaire (C-SSRS, Baseline version);
- Blood sampling for laboratory assessment (hematology, biochemistry, virology);
- Urine pregnancy test, if applicable;
- Adverse event reporting.

Prior to randomization, results of all baseline assessments (except hematology, biochemistry and virology results, which will become available only later) will be reviewed. Subjects who do not meet all inclusion criteria and / or who meet one or more of the exclusion criteria are excluded at this point and will not be randomized (screening failures).

Eligible subjects are randomly allocated to either the active treatment (AM-111 0.4 or 0.8 mg/mL) or placebo.

After receiving the single dose of IMP, all subjects will be advised to avoid noisy situations until FUV4, and to protect the ear canal and middle ear of the treated ear from water exposure until the tympanic membrane is closed again.

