^{*} Pure tone audiograms measured in subjects presenting within the first 24 hours from ISSNHL onset have to be confirmed by a second measure that is conducted, at the earliest, 24 hours after the onset of ISSNHL. This new confirmatory assessment will serve as baseline value.

^{**} Speech audiometry, spontaneous nystagmus and balance test will be assessed, at the earliest, 24 hours after ISSNHL onset, and this measurement will serve as baseline value.

For the background therapy the investigator prescribes or provides prednisone, prednisolone or methylprednisolone, and the background therapy documentation card documenting the compliance will be handed out to the subject.

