Appendix 1: Tinnitus Presence or Absence

TV (D0): Baseline assessment regarding the presence or absence of tinnitus

Subject instruction at baseline (to be read by the investigator to the patient):

If someone hears sound or noise in one or both ear(s) or in the head which no one else can hear, then this is called tinnitus. If you are affected, you may hear a sound such as ringing, humming, hissing, buzzing, roaring or other sounds. You may hear the sounds all of the time or some of the time. The sound may appear to be louder or softer to you during the day or from day to day, that is the tinnitus loudness may vary, or the loudness is always more or less the same. Tinnitus does not have to be annoying, and it frequently disappears sometime after experiencing acute hearing loss. However, tinnitus may be very annoying to some people — especially if it persists, or at some particular times, for example when trying to relax or fall asleep.

[figure not shown]

The Investigator will further investigate whether the tinnitus is related to the ISSNHL incident or a pre-existing condition.

D3 – D91: Tinnitus presence or absence

For follow-up assessments, questions "Are you experiencing tinnitus right now" and "Have you experienced tinnitus in the past week" will be answered by subjects at trial visits and on a weekly basis in a diary.

As explained to you by the Investigator, tinnitus is a sound or noise that you can hear in one or both ear(s) or in the head which no one else can hear. If you are affected, you may hear a sound such as ringing, humming, hissing, buzzing, roaring or other sounds. You may hear the sounds all of the time or some of the time. The sound may appear to be louder or softer to you during the day or from day to day, that is, the tinnitus loudness may vary, or the loudness is always more or less the same. Tinnitus does not have to be annoying, and it frequently disappears sometime after experiencing acute hearing loss. However, tinnitus may be very annoying to some people – especially if it persists, or at some particular times, for example when trying to relax or fall asleep.

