7.2 KEY DEFINITIONS

Baseline:

Baseline is defined as pre-intratympanic administration assessment or baseline is the last non-missing assessment value before the first dose of study IMP. This definition will be used for all baseline and change from baseline analyses, unless specified otherwise.

Pure tone audiograms measured in subjects presenting within the first 24 hours from ISSNHL onset have to be confirmed by a second measure that is conducted, at the earliest, 24 hours after the onset of ISSNHL. This new confirmatory assessment will serve as baseline value.

Speech audiometry, spontaneous nystagmus and balance test will be assessed, at the earliest, 24 hours after ISSNHL onset, and this measurement will serve as baseline value.

First Dose Date:

For subjects randomized to AM-111, the first dose date will be defined as the date of TV Day 0.

Study Day:

Study day is defined as the number of days from the date of first dose to the event/visit date. It is calculated as follows: Study Day = Event or Visit Date - First Dose Date.

Hence, the date of first dose is referred to as Day 0. The previous day is Day -1.

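### The 24-hour repeat of baseline tests leaves out tinnitus, so tinnitus that stops before injection can be counted as complete remission

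*Protocol*

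**What the plan says.** **Hearing and vestibular baselines.** Protocol 5.1, 6.6.5.3 and 7.1 require a new pure tone audiogram, at least 24 hours after onset, for anyone first tested inside 24 hours: "This new confirmatory assessment will serve as baseline value". The double-asterisk note in 7.1 adds: "Speech audiometry, spontaneous nystagmus and balance test will be assessed, at the earliest, 24 hours after ISSNHL onset". SAP 7.2 carries the same list: "Speech audiometry, spontaneous nystagmus and balance test will be assessed, at the earliest, 24 hours after ISSNHL onset, and this measurement" is then the baseline. Footnote 5 of Table 1 reads: "Assessment to be repeated, at the earliest, 24 hours from onset if subject presenting within the first 24 hours from ISSNHL onset". It is attached to speech audiometry, nystagmus and balance and, in the SAP's copy of the table, to pure tone audiometry. Protocol 6.6.5.3 gives the reason for repeating the audiogram: "The high possibility of spontaneous remission early after ISSNHL onset may otherwise lead to the inclusion of patients who would recover on their own".

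**Tinnitus baseline.** In the 7.1 list the item "Tinnitus presence or absence and numerical rating scales" carries neither asterisk mark, and footnote 5 is on neither tinnitus row of Table 1. Protocol 6.6.4 sets the timing at the Treatment Visit: "At Treatment Visit, the questionnaires may be completed after audiology assessment, but have to be completed in any case prior to IMP administration". Protocol 6.3 lets a tinnitus evaluation made before consent stand only if it was done on the day of treatment. Protocol 7.1 allows baseline procedures to fall on different calendar days.

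**Use of the baseline.** Complete tinnitus remission at FUV4 is assessed among subjects with ISSNHL-related tinnitus at baseline (Protocol 10.1.2, SAP 5.1.2.2). SAP 7.2 takes the last available value before dosing as baseline. SAP 9.2.2 and 12 accept a negative answer on tinnitus presence as remission, without zero TLQ and TAQ ratings.

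**The concern.** The repeat rule guards against measuring baseline during early spontaneous recovery. The protocol expects tinnitus to resolve spontaneously too: Appendix 1 tells subjects that "it frequently disappears sometime after experiencing acute hearing loss". Yet the rule leaves out the one symptom whose complete disappearance is an endpoint.

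Baseline tinnitus fixes the denominator of that endpoint. It is also the reference for the change in loudness and annoyance (SAP 16, Table 14.2.3.2.2). If the rating is made at the first session and not renewed, nothing planned shows whether tinnitus was still present at injection. Hearing and tinnitus baselines in the same subject can also come from different times. The SAP is now descriptive only, so the per-arm remission rates are themselves the result.

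**Working it through.** **1. Timing rules side by side**

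| Baseline item | 24-hour rule | Other timing limit |
|---|---|---|
| Pure tone audiometry | Yes (5.1, 6.6.5.3, 7.1) | Routine audiogram: at most 2 h before consent and 5 h before IMP |
| Speech audiometry | Yes (6.6.5.4, 7.1, SAP 7.2) | Same |
| Nystagmus, Romberg | Yes (6.6.6, 7.1, SAP 7.2) | If done before consent: day of treatment (6.3) |
| Tinnitus presence, TLQ, TAQ | None | Before IMP (6.6.4); if done before consent: day of treatment (6.3) |

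**2. One subject traced.** The subject is first seen 6 h after onset, consents and reports tinnitus. The audiogram must be redone at 24 h or later, so the tinnitus rating predates the audiometric baseline by at least 24 − 6 = 18 h. Treatment is allowed up to 72 h after onset, so the rating can precede injection by up to 72 − 6 = 66 h. If no second rating is made, the 6 h answer is the last pre-dose value and hence the SAP baseline.

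**3. What misclassification requires.** All of these must hold:
- consent and tinnitus rating at a session before 24 h;
- no second rating before IMP;
- tinnitus stopping in between;
- hearing still meeting the entry thresholds at the repeat audiogram;
- tinnitus absent at FUV4.

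**4. Size, on assumed inputs.** There is no figure in the plan to reproduce, and every rate below is an assumption. Let f be the share of subjects with baseline tinnitus who are rated only before 24 h, and q the share of those whose tinnitus stops before injection. The misclassified share is c = f × q. With true remission p, the observed rate is c + (1 − c)p, and the observed difference is (1 − c) times the true difference. Take true rates of 30% (placebo) and 50% (active). Power is for a two-sided 5% comparison of two proportions at the planned 100 per arm. With 56 enrolled, 56/3 ≈ 19 per arm.

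| f | q | c | Subjects per arm (100 / 19) | Placebo | Active | Difference (points) | OR | Power at 100 per arm |
|---|---|---|---|---|---|---|---|---|
| – | – | 0 | 0 / 0 | 30.0% | 50.0% | 20.0 | 2.33 | 82.8% |
| 10% | 5% | 0.5% | 0.5 / 0.1 | 30.35% | 50.25% | 19.9 | 2.32 | 82.3% |
| 20% | 10% | 2% | 2.0 / 0.4 | 31.4% | 51.0% | 19.6 | 2.27 | 80.9% |
| 40% | 20% | 8% | 8.0 / 1.5 | 35.6% | 54.0% | 18.4 | 2.12 | 74.8% |

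Highest row: c = 0.40 × 0.20 = 0.08; placebo 0.08 + 0.92 × 0.30 = 0.356; active 0.08 + 0.92 × 0.50 = 0.54; difference 0.92 × 20 = 18.4 points.

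For given f and q these are upper bounds. They treat every pre-dose remitter as still free of tinnitus at FUV4, and every subject as having baseline tinnitus.

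**The case against.** The sentence in Protocol 6.6.4 equally allows the forms to be completed after the repeat audiogram, just before injection. SAP 7.2 would then take that later rating, and a subject whose tinnitus had stopped would leave the denominator. This stands: the plan permits the error but does not cause it. A reader might infer that all tinnitus stopping before injection is counted as remission, but the documents do not support that.

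Nor is completion before IMP the only timing limit. Protocol 6.3 bars a pre-consent tinnitus evaluation from an earlier day. This also stands, and it confines the gap mainly to ratings made after consent, which have no such limit.

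A reader might further infer a bias toward AM-111. The documents point the other way. Baseline assessments are completed before randomization (Protocol 6.7, 7.1) and the trial is double-blind, so the error should be equal across arms in expectation. With about 19 per arm a chance imbalance is possible, but it has no preferred direction.

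The stated reason for the repeat concerns audiometry and the inclusion of subjects who would recover anyway. Tinnitus is not an entry criterion, so that reason extends to it by analogy only. Finally, the wording of the baseline tinnitus question is not visible. If it covers a recall period, re-rating would not remove every affected subject.

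What remains is that no text requires a tinnitus rating at or after the repeat audiogram, and the rule taking the last pre-dose value helps only if a second rating exists.

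**Conclusion.** The omission is confirmed in the protocol text, Table 1 and SAP 7.2. A first-session tinnitus rating made after consent can validly stand as baseline, and tinnitus that resolves before injection and is absent at FUV4 can then be reported as complete remission.

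The effect is to raise every arm's remission rate and slightly dilute the contrast. On the assumed inputs, 0.5-8% of the denominator is affected, and an odds ratio of 2.33 would be seen as 2.32 to 2.12. With 56 enrolled this is roughly 0.1 to 1.5 subjects per arm. One subject in 19 moves an arm's rate by 1/19, about 5 points, and by more if fewer subjects had tinnitus at baseline. The true size depends on how many subjects were rated only before 24 h, which the documents do not give.

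The endpoint is one of the other secondary endpoints and the analysis is descriptive. This is a cheap improvement of modest impact.

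**What to change.** **Protocol, for any reuse of this design.** Extend Table 1 footnote 5 and the double-asterisk note in 7.1 to tinnitus presence, TLQ and TAQ, re-rated at the confirmatory audiometry session and before IMP. Recruitment has stopped, so this changes nothing for the 56 subjects enrolled.

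**SAP 7.2.** Name that rating as the tinnitus baseline.

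**Subjects already enrolled.** Protocol 7.1 asks for the times of baseline assessments to be recorded on the CRF. Use them to flag subjects whose only tinnitus rating predates their audiometric baseline. Show the FUV4 remission rate and the TLQ/TAQ change by arm with and without them.

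**Cost.** One short form repeated at a session the subject already attends, one flag and one extra sensitivity row.
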